Results: During the 7 month study period, the SC screened 418 patients for eligibility criteria, including but not limited to pain score ≥ 4 . Following screening, 59 were deemed eligible, and 46 consented and randomized to Acupuncture (n=23) or Usual Care (n=23) with 2 subjects in the Acupuncture group withdrawing after consent. The average age was 36.3 (15.5 SD), 78% were female and 55.0% were non-white. Those randomized to Acupuncture reported a pre-treatment pain score of 8.18 (SD 1.62), a 60-min post-treatment pain decrease of -3.0 units (SD 2.51), decrease at ED discharge of -2.71 units (SD 1.86) and reduction at 30-day follow-up of -5.28 (3.0) units. The Usual Care group had a pre-treatment pain score of 7.91 (SD 1.41), a 60-min post-treatment pain decrease of -1.56 units (SD 2.37), decrease at ED discharge of -2.53 units (SD 2.27) and reduction at 30-day follow-up of -3.41 (4.0) units. Since the aim of the pilot RCT was to determine feasibility, as a result no between-group analyses were conducted.

“Lessons learned” included that: (1) an RCT was feasible in a busy ED; (2) ~14% (59/418) of screened patients met eligibility criteria; (3) ~78% (46/59) of eligible patients consented to participate; (4) ~78% of both Acupuncture and Usual Care patients provided post-treatment and ED discharge scores; (5) electronic data collection was feasible for blinding the study team assessor to patient scores; but (6) only ~35% (16/46) of both groups completed the 30-day follow-up via phone call, so new methods for follow-up are needed.

Observational Study 2: University Hospitals (UH) Broadview Heights ED

Upon joining University Hospitals & Case Western Reserve University in Oct 2018, [name] launched a 4-week observational study to replicate/extend the procedures used in the ANW ED observational study (above). Changes included the use of auricular ear seeds to potentially extend pain relief, and reducing 30 day follow-up to a 1-week (+/- 2 days) phone call. Goals were to: (1) determine whether auricular ear seeds would be tolerated by patients; and (2) preliminarily explore if ear seeds provided extended pain relief at 1-week.

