Results: During the study period, the acupuncturist was referred and then approached 24 patients. Informed consent was obtained from 79% (19/24) of patients. The average pain pre-treatment score was 4.68, and the post-treatment change was a decrease of -2.07 units and ED discharge change was a reduction of -1.68 units. Ear seeds were used in a majority (14/19) of patients. Phone calls were only successful in 8 patients due to the holidays. Seven of eight patients reported retaining the ear seeds in place until the 1-week follow-up. The 1-week pain reduction was of -3.68 units.

“Lessons learned”: (1) extended auricular therapy (ear seeds) was well tolerated by patients; and (2) ear seeds may provide pain relief at 1-week.

Rationale for the Proposed Study: Despite these positive findings in the pilot RCT and two observational studies, there are several issues that need to be addressed before proceeding to a future definitive study. First, a better understanding of process outcomes such as recruitment/reach, stakeholder acceptability, and intervention fidelity are needed to ensure optimal recruitment and minimal patient attrition. We will assess these outcomes carefully in this study. We are also introducing several improvements at the outset. For example, to improve retention, we will reduce the follow up period to 1-week and use text messaging features of REDCap. To improve fidelity, we will develop a ‘responsive’ manualized-based intervention (consensus protocol with options) and a corresponding fidelity assessment tool. Finally, intervention observations and interviews with stakeholders (ED providers and administrators, ED

patients and study acupuncturists) will provide valuable explanatory data regarding barriers and facilitators to implementation that will be useful for a future, multi-site, pragmatic, definitive RCT. **Taken together, our understanding of the current gaps in the literature, promising results from our observational studies, and our operational knowledge gained from the pilot RCT combine to provide the necessary evidence and expertise to support the conduct of the proposed, multi-site feasibility clinical trial.**

Aim 1: Develop a Manualized Acupuncture Intervention

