7.3 Adverse Events and Serious Adverse Events

An adverse event (AE) is any unfavorable and unintended diagnosis, symptom, sign (including an abnormal laboratory finding), syndrome or disease which either occurs during the study, having been absent at baseline, or if present at baseline, appears to worsen. Adverse events are to be recording regardless of their relationship to the study intervention and through follow-up.

A serious adverse event (SAE) is any untoward medical occurrence that results in death, is life threatening, requires inpatient hospitalization or prolongation of existing hospitalization, results in persistent or significant disability/incapacity, or is a congenital anomaly.

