7.4 Reporting Procedures

RESPONSIBLE INDIVIDUALS

The site Principal Investigator (PI) is responsible for assessing all AE and SAEs. The site PI will monitor AE reporting and complete the AE PI Report in the ACUITY REDCap for events reported at the 1 and 4 week follow-ups. Research staff are responsible for documenting the events determined to be an AE or SAE, as well as any adverse events occurring in the ED or reported by a subjects physician, in the ACUITY Subject AE Log and reporting these events to the Clinical Coordinating Center within the required timelines.

PROCEDURES

Reporting Adverse Events: The PI or their delegated research staff will review reported events to determine if they qualify as an AE/SAE and assign causality and severity/intensity in REDCap. Research staff will document AE on the Subject ACUITY AE and External AE Summary logs after becoming aware of the event. Subject AE logs will be filed with the individual subject's research files. The External Summary AE log must be provided to the Clinical Coordination Center upon request, including for Quality Assurance, sIRB Continuing Review, and Study Close Out.

Reporting Serious Adverse Events: Research staff will document SAE on the Subject ACUITY AE log after becoming aware of the event. The PI or their delegated research staff will review, sign off on SAE

and assign causality and severity/intensity. If the event satisfies all three of the FDA requirements for reporting SAEs it will be reported to the IRB;

- a. Serious
- b. Unanticipated, and
- c. Related to study product or study procedures

If the event is clarified as an SAE and deemed reportable to the IRB, delegated research staff will report event to the IRB within 5 days of being notified of event via the University Hospital's Cleveland Medical Center's (UHCMC) IRB's "Reportable New information Smart Form" (RNI). If more information becomes available to CIHN regarding SAE, delegated research staff will inform and follow-up with IRB.

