Since the goal of the current U01 proposal is to test feasibility of the study procedures used in the single-site pilot RCT, we plan to enroll 150 participants (50 per site). Additionally, a pilot 5 subjects per site will be consented and brought through the study protocol, but will not be counted toward the n=150 enrollment. The 150 enrollment number is both pragmatic for achieving our goals related to assessing feasibility, acceptability and fidelity and is about 25% of the eventual sample size required for a future definitive non-inferiority study. We contend that our ability to recruit about 25% of the anticipated sample size for a future definitive RCT would demonstrate our collective capabilities to recruit across 3 EDs across the United States..

Treatment Assignment Procedures

Random assignments will be made by the study statistician in permuted blocks of size 2 and 4. The block size will also be randomly generated to minimize correct prediction of assignments and preserve approximate balance between groups, using the rand function in SAS. Administrative personnel from the BraveNet Coordinating Center will prepare each randomization packet in a sealed envelope and send these to each site in batches. A date/signature label will be placed over the envelope seal. Randomization envelopes will be stored in locked cabinets and opened by study staff (SC or RA) after completion of the informed consent process and baseline data collection.

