10.2 Data Management

In our pilot RCT, we developed and successfully used a basic electronic data collection tool (StudyTRAX). In Year 1, we will build a comprehensive study management database and data collection platform using REDCap and confirm the ability to blind assessors to patient scores and text message subjects for the 1-week follow-up assessment. Our team has successfully used REDCap for multisite data collection in the BraveNet PBRN as well as across [name] multi-clinic studies.

Informed consents and HIPAA authorizations will be collected as hard copy paper documents; these will be kept by the study team in individual patient binders in locked filing cabinets of a secure, badge-access location at each site.

Demographic and baseline data will be collected both by the SC and through EHR data extraction at baseline. The data collected by research staff will be entered directly into an electronic data collection tool. There will be no hard copies of this data.

Patient Reported Outcomes (PROs) (pain intensity and anxiety) will be collected by study staff (SC or RA), rather than by the acupuncturists delivering treatments. All PROs will be entered directly by the study participant on a tablet via REDCap and will disappear from view once entered so neither the participant nor research staff will have access to the scores. The scores will then be exported to a password protected database. There will be no hard copies of this data.

Satisfaction data will be collected as part of ED-discharge and at 1-week and 4-week follow up for patients. ED staff will complete a one-time brief survey at the end of the enrollment period.

EHR data will be electronically extracted by each site with HIPAA protected identifiers as limited datasets. The data extracted from EHR will be verified by MRN and date with our electronic platforms. EHR extracted data will include demographic data, pain medication use in the ED, and opioid prescriptions at discharge. Both [name] and [name] have extensive experience in use of EHR data. There will be no hard copies of this data.

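### No step establishes adverse-event status after discharge for patients who answer neither follow-up, so serious events among them may be missed

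*Combined protocol and SAP*

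**What the plan says.** Section 7.3 states: "Adverse events are to be recording regardless of their relationship to the study intervention and through follow-up". It counts death and inpatient hospitalization among the serious events. Section 7.2, which should describe how safety is assessed, is marked N/A.

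Section 7.4 gives the routes by which events become known. For the period after discharge, the site PI is to "complete the AE PI Report in the ACUITY REDCap for events reported at the 1 and 4 week follow-ups". Staff also log events that arise in the ED and events that a patient's physician reports.

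The follow-up form in Appendix B asks whether illness, pain or health problems are new or worse since discharge. It has no item on hospital admission or return to an ED.

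Sections 6.2.4 and 6.2.5 collect the follow-ups by text or email, or by phone call, at 1 and 4 weeks, each with a 4-day window either way. Section 4.3 pays $25 for each one completed.

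Section 10.2 describes a site EHR extraction that is checked by record number and date: "EHR extracted data will include demographic data, pain medication use in the ED, and opioid prescriptions at discharge". All the listed items concern the index visit.

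On past response, section 2.2 reports for the pilot trial: "only ~35% (16/46) of both groups completed the 30-day follow-up via phone call, so new methods for follow-up are needed".

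**The concern.** The plan sets a recording duty that runs to the end of follow-up, yet it actively looks for events only among patients who reply. A patient who has died cannot reply, and one who has been admitted may find it harder to. For a patient who answers neither follow-up, an event reaches the log only if a physician or someone else happens to report it.

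The protocol's own earlier work shows that non-response is foreseeable. Sections 6.2.4 and 6.2.5 set no number of contact attempts for these follow-ups, while section 4.3 allows up to five attempts to schedule the qualitative interview. That interview is offered only to the acupuncture arm, so staff may also hear of events incidentally in one arm and not in the other.

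At stake are the completeness of AE and SAE totals and the picture given to the independent monitoring committee (sections 7.6 and 10.3.4). The procedure itself also matters, because the primary objective is to refine procedures for a definitive trial.

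**Working it through.** **Inputs from the documents**
- Pilot trial, 30-day phone follow-up: 16 of 46 (section 2.2).
- Second observational study, 1-week phone call: "Phone calls were only successful in 8 patients due to the holidays", out of 19 who consented (section 2.2).
- Planned enrolment: 150, with 15 further pilot patients not counted (section 9.2).

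**Inputs assumed**
- The documents give no SAE rate. I take p = 1%, 2% and 5% over 4 weeks, independent of response.
- Response in this trial is unknown. I take 35%, 70% and 90%.
- No other route finds the event. This is an upper bound on what is missed under independence.

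**Step 1: the plan's own figure.** 16/46 = 34.8%, which agrees with the stated 35%. The exact 95% confidence interval is 21.4% to 50.2%. For the second study, 8/19 = 42% (20% to 67%).

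**Step 2: patients with no report.** Non-responders = 150 × (1 − response). At 34.8% this is 97.8, or about 98. Over the confidence interval it runs from 150 × (1 − 0.502) = 75 to 150 × (1 − 0.214) = 118. At 70% it is 45 and at 90% it is 15.

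**Step 3: chance that at least one SAE falls among them.** P = 1 − (1 − p)^n, where n is the number of non-responders. For p = 2% and n = 98, P = 1 − 0.98^98 = 86%.

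| Response | n | p = 1% | p = 2% | p = 5% |
|---|---|---|---|---|
| 35% | 98 | 63% | 86% | 99% |
| 70% | 45 | 36% | 60% | 90% |
| 90% | 15 | 14% | 26% | 54% |

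The expected number of SAEs among non-responders at p = 2% is n × p: 1.96, 0.90 and 0.30.

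**Step 4: credit for having two follow-ups.** If the two earlier rates applied to the two contacts, and replies were independent, the share answering at least one would be 1 − (1 − 0.348)(1 − 0.421) = 62%. That leaves 150 × 0.378 = 57 silent, and P = 1 − 0.98^57 = 68% at p = 2%. Independence is optimistic, and a reply at 1 week says nothing about weeks 2 to 4.

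**Step 5: effect of a record search.** If the search finds a share c of the events, replace p by p(1 − c). At p = 2%:

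| Response | no search | c = 50% | c = 80% |
|---|---|---|---|
| 35% | 86% | 63% | 33% |
| 70% | 60% | 36% | 17% |
| 90% | 26% | 14% | 6% |

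The documents give no value for c, so both values are assumptions.

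**The case against.** The strongest reply is that the pilot figure belongs to a different procedure. It came from one site and one phone call at 30 days, and the protocol drew the lesson that other methods were needed. This trial adds text and email, pays for each follow-up, and treats refusal to give contact details as declining to take part. A reader might infer that about 35% will answer here. The documents do not support that, and the reply stands in full on this point.

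A reader might also infer that a silent patient will be recorded as event-free. No section says so. Sections 9.5 and 9.5.1 plan to track retention and missing data at each time point, by arm and site, so the number lost would be visible. What is absent is a rule for their safety status.

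Other routes exist. A physician may report an event, staff must log any SAE they learn of, and both follow-up forms ask about the whole time since discharge. Some acupuncture patients will also be interviewed at about 3 weeks. These routes mean that events may be missed, not that they will be. None of them is designed to cover silent patients in both arms.

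The effect on IRB reports is small. Section 7.4 sends an SAE there only if it is serious, unanticipated and related, and few all-cause events after a single acupuncture session are likely to qualify.

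Finally, the manual of procedures is not among the documents and may say more about non-responders. The consent pages were removed from the review copy, so their cover for a later record search cannot be checked.

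**Conclusion.** The point holds as a gap in ascertainment. The plan requires recording through follow-up, gives one active source that depends on a reply, and has no step for patients who do not reply. Serious events in those patients may be missed, and AE and SAE totals may be understated.

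The size depends mainly on response. At an assumed 2% SAE risk, the chance that at least one SAE falls among non-responders runs from about 26% at 90% response to 86% at 35%. These figures rest on SAE risk being independent of response and on no capture elsewhere. The first assumption probably makes them too low if sicker patients reply less, and the second makes them too high. They illustrate why the gap matters even with good follow-up, and they are not predictions for this trial. The tempting stronger conclusion, that a known number of serious events will be lost, goes beyond what the documents can show.

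The change is worth making because it is specific and inexpensive.

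**What to change.** - **Sections 7.2 and 7.4:** replace the N/A with a stated method. For every randomised patient in both arms, search the site EHR for deaths, inpatient admissions and ED return visits from ED discharge through day 32 (28 days plus the 4-day window). The site PI assesses each hit under section 7.3.
- **Section 10.2:** add these three items and the later time window to the EHR extraction.
- **Reporting:** give AEs and SAEs by arm and by source (survey, EHR, other). Give by arm the number of patients whose safety status remains unknown.

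The cost is a later and wider data pull for 150 patients and a few more records for the site PI to review. The search mainly sees care within the site's own health system, so some events will still be missed. Whether the consent and HIPAA authorization cover it must be confirmed before it starts.

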7.5 Follow-up for Adverse Events

Delegated research staff is responsible for all follow-up associated with AEs and SAEs and reporting this information to the IRB until the AE occurs.

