7. SAFETY ASSESSMENTS

Monitoring of the study for AEs will be continuous throughout the study. In the event of an AE or SAE, it will be reported to the UH IRB in compliance with UH IRB standards.

The investigative team will monitor the data security, data integrity, and patient safety. The study team will meet at least every 2-4 weeks to assess for adherence to protocol and review any safety events. Based on our successful prior experience with our observational study and RCT), the likelihood of

adverse physical, psychological, social, and legal risks is expected to be very small. Acupuncture carries very slight risks for:

- Bleeding,
- Bruising,
- Fainting (acushock)
- Needling pain

In the event a patient experiences an adverse event (AE), they will be treated by providers in the site ED and will have access to emergency response equipment as necessary.

Acupuncture involves inserting thin, sterile needles in the skin. The needles are not inserted into the skin very far. Sometimes the needles cause slight discomfort or minor bleeding. Any acupuncturist who provides treatments in this study will be licensed by the state in which they practice.

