7.1 Specification of Safety Parameters

N/A

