7.2 Methods and Timing for Assessing, Recording, and Analyzing Safety Parameters

N/A

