SECTION 4 – Anxiety

2. Please rate your anxiety, **right now**, on a scale of 0 to 10, where 0 is no anxiety, and 10 is the worst anxiety imaginable.

0	1	2	3	4	5	6	7	8	9	10
---	---	---	---	---	---	---	---	---	---	----

SECTION 5 – Randomization (logic to open up this form)

→ Build randomization module into REDCap

POST ACUPUNCTURE FORM – Patient facing, blinded to coordinator

INSTRUCTIONS: “There are some additional questions for you to answer on this iPad or your phone. I will be here to answer any questions you may have. Please do not show me the answers to these questions. Please hand the iPad back to me when you are done or let me know when you have completed the survey on your phone.”

SECTION 1 – Pain

1. Please rate your pain, **right now**, on a scale of 0 to 10, where 0 is no pain, and 10 is the worst pain imaginable.

0 1 2 3 4 5 6 7 8 9 10

SECTION 2 – Anxiety

2. Please rate your anxiety, **right now**, on a scale of 0 to 10, where 0 is no anxiety, and 10 is the worst anxiety imaginable.

0 1 2 3 4 5 6 7 8 9 10

SECTION 3 – Satisfaction

3. How satisfied are you with how your pain was managed during your ED visit?

- a. Very Unsatisfied
- b. Somewhat Unsatisfied
- c. Neutral
- d. Somewhat Satisfied
- e. Very Satisfied

4. Overall how satisfied are you with your treatment during your ED visit?

- a. Very Unsatisfied
- b. Somewhat Unsatisfied
- c. Neutral
- d. Somewhat Satisfied
- e. Very Satisfied

SECTION 4 – ED Impact (Acupuncture Arm Only)

1. Please rate the impact of acupuncture on your ED visit today.

- a. Very Negative
- b. Somewhat Negative
- c. Neutral
- d. Somewhat Positive
- e. Very Positive

POST ACUPUNCTURE FORM – Coordinator facing, information gathered from Acupuncturist

SECTION 4 – Ear Seeds (Acupuncture Arm Only)

1. Did the participant receive ear seeds in the ER
 - a. Yes
 - b. No

POST USUAL CARE FORM – Patient facing, blinded to coordinator

INSTRUCTIONS: “There are some additional questions for you to answer on this iPad or your phone. I will be here to answer any questions you may have. Please do not show me the answers to these questions. Please hand the iPad back to me when you are done or let me know when you have completed the survey on your phone.”

SECTION 1 – Pain

1. Please rate your pain, **right now**, on a scale of 0 to 10, where 0 is no pain, and 10 is the worst pain imaginable.

0 1 2 3 4 5 6 7 8 9 10

SECTION 2 – Anxiety

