9. OTHER [FREE TEXT]

10. (Acupuncture Arm Only) Since your discharge from the Emergency Room on [er_visit_date], have you received acupuncture?

- a. Yes
- b. No
- c. Do not know

i. If yes, was the acupuncture effective to relieve your symptoms?

1. Yes
2. No
3. Do not know

11. Since your discharge from the Emergency Room on [er_visit_date], have you experienced new or worsening ILLNESS?

- a. No

b. Yes

IF YES PLEASE DESCRIBE [FREE TEXT]

12. Since your discharge from the Emergency Room on [er_visit_date], have you experienced new or worsening PAIN?

- a. No
- b. Yes
- c. Don't know

IF YES PLEASE DESCRIBE [FREE TEXT]

13. Since your discharge from the Emergency Room on [er_visit_date], have you experienced new or worsening HEALTH ISSUES?

- a. No
- b. Yes
- c. Don't know

IF YES PLEASE DESCRIBE [FREE TEXT]

Instructions: Below are some questions that ask you to rate how you are feeling right now.

SECTION 2 – Pain

1. Please rate your pain, right now, on a scale of 0 to 10, where 0 is no pain, and 10 is the worst pain imaginable.

0 1 2 3 4 5 6 7 8 9 10

SECTION 3 – Anxiety

2. Please rate your anxiety, right now, on a scale of 0 to 10, where 0 is no anxiety, and 10 is the worst anxiety imaginable.

0 1 2 3 4 5 6 7 8 9 10

SECTION 4 – Satisfaction

3. “How satisfied were you with how your pain was managed during your ER visit” on the 5-point Likert scale.

- a. Very Unsatisfied
- b. Somewhat Unsatisfied
- c. Neutral
- d. Somewhat Satisfied
- e. Very Satisfied

4. "Overall how satisfied were you with your treatment during your ER visit?" on the same Likert Scale.
 - a. Very Unsatisfied
 - b. Somewhat Unsatisfied
 - c. Neutral
 - d. Somewhat Satisfied
 - e. Very Satisfied

FOLLOW UP FORM for 1 week F/U (Acupuncture Arm Only, if Post Acupuncture Form Ear Seeds question is "Yes")

SECTION 5 – Ear Seeds

1. Before this follow-up, did you remove the ear seeds that you received in the ER on [er_visit_date]
 - a. Yes
 - i. If yes, when did you remove them? [enter date]
 - b. No (if no, you should remove them now)
2. After your ER discharge, did you ever stimulate/touch the ear seeds yourself for pain relief?
 - a. Yes
 - b. No
3. Any comments on the ear seeds [FREE TEXT]

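### Section 7.5 gives no usable end point for adverse-event follow-up, and no ED form in Appendix B asks about the four listed needling reactions

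*Combined protocol and SAP*

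**What the plan says.** Section 7 states that "Monitoring of the study for AEs will be continuous throughout the study" and provides for a study-team review of safety events at least every 2 to 4 weeks. Sections 5.1 and 7 both introduce a list with the words "Acupuncture carries very slight risks for" and name four items: bleeding, bruising, fainting and needling pain.

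The two sections that would normally set out the method, headed "7.1 Specification of Safety Parameters" and "7.2 Methods and Timing for Assessing, Recording, and Analyzing Safety Parameters", are marked N/A.

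Section 7.3 defines AEs and SAEs and says "Adverse events are to be recording regardless of their relationship to the study intervention and through follow-up". Section 7.4 has the site PI assess all AEs and SAEs and complete a report for events given at the 1- and 4-week contacts. It has staff log ED events once they become aware of them, and has later SAE information passed to the IRB. Section 7.5 is a single sentence. It makes delegated staff responsible for all AE and SAE follow-up and for "reporting this information to the IRB until the AE occurs".

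Section 10.1 refers to Appendix B for the RCT data collection forms. There, item 11 of the follow-up form asks whether since discharge "have you experienced new or worsening ILLNESS", and items 12 and 13 ask the same about pain and health issues. The coordinator-facing Post Acupuncture form is described as "information gathered from Acupuncturist" and contains one question, on ear seeds.

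**The concern.** Two separate weaknesses bear on the same quantity, the trial's account of acupuncture harms.

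The first is an operative safety rule that cannot be carried out. The end point it names is the moment at which follow-up of an event begins.

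The second is that the four reactions the protocol itself expects have no field on the forms completed in the ED, where they would happen. If such reactions are recorded only when someone happens to notice them, a low count may reflect a low rate or incomplete capture, and the data cannot tell these apart. The primary objective (Section 1.1) is to refine procedures for a definitive multi-site trial. Harm capture is one of those procedures, so the gap could be carried forward.

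**Working it through.** The plan states no figure on this point, so the check is mainly a comparison of sections and forms.

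**1. Is a follow-up end point given anywhere else?**
- 7.3 says which events are recorded and for how long. It does not say how long a recorded event is followed, or to what outcome.
- 7.4 covers assessment, logging and reporting. Its only forward-looking rule, on new information, is limited to SAEs.
- 7.5 is the only section on follow-up, and its end point is event onset.

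For non-serious AEs, a group that would ordinarily include most of the listed reactions, no workable end point remains.

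**2. Do the IRB reporting statements agree?**
- Sections 5.1 and 7: an AE or SAE will be reported to the UH IRB, in line with that IRB's standards.
- Section 7.4: an event goes to the IRB if it is serious, unanticipated and related.
- Section 7.5: IRB reporting is attached to AEs and SAEs alike.

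The reference to IRB standards may be meant to import the restriction in 7.4, but the text does not say so.

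**3. What do the Appendix B forms ask?**

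| Form | Content after treatment | Listed reactions asked about |
|---|---|---|
| Post Acupuncture, patient | pain, anxiety, satisfaction, ED impact | 0 of 4 |
| Post Acupuncture, coordinator | ear seeds yes/no | 0 of 4 |
| Post Usual Care | pain, anxiety, satisfaction | not applicable |
| Discharge, acupuncture | pain, anxiety, satisfaction, ED impact | 0 of 4 |
| Discharge, usual care | pain, anxiety, satisfaction | not applicable |
| 1- and 4-week, both arms | three general harm questions with free text | none by name |

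The acupuncturist's session record (Section 5.1) lists points, needles, times and response to stimulation. Adverse reactions are not named.

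**4. Do the follow-up questions fill the gap?** They ask about new or worsening problems since discharge. A faint, a bleed or needling pain that starts and resolves in the ED lies outside that window. A bruise that lasts might still be mentioned. The answers also depend on retention: in the earlier single-site pilot RCT, 16/46 = 35% completed the 30-day contact (Section 2.2), although this trial uses new contact methods.

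**5. Illustration of scale.** If every treated patient is asked and none reports a reaction, the one-sided 95% exact upper bound on the rate is 1 − 0.05^(1/n).
- n = 75 (150 split evenly, all treated): 1 − 0.05^(1/75) = 3.9%.
- n = 60 (assumed, because Sections 3 and 5.1 allow that some acupuncture-arm patients will not be treated): 1 − 0.05^(1/60) = 4.9%.

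The formula requires that each patient's status is known. When events are recorded only on awareness, that condition is not met and no such bound follows.

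**The case against.** A reader might infer that acupuncture harms are neither solicited nor followed in this trial. The documents do not support that. Three general harm questions go to both arms at each of two contacts. The site PI reviews the answers, and causality and severity are assigned. ED events have a named log, AEs are recorded through follow-up whatever their cause, and later SAE information goes to the IRB. Patients given ear seeds also have a free-text comment field at 1 week.

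Three further points have force.
- The wording of 7.5 is probably a drafting slip. The same sentence gives staff responsibility for all AE follow-up, and the limiting clause can be read as applying only to IRB reporting. It would be too strong to say that outcomes will go uncaptured in practice. The slip still leaves the only follow-up section without an end point.
- Appendix B is titled as screening and patient-reported outcomes. The AE log, the AE PI report, the acupuncturist's session record, the ED Visit Checklist and the manual of procedures are named but not reproduced, and any of them might prompt for reactions. The finding must therefore be limited to the ED forms reproduced in Appendix B.
- A licensed acupuncturist is present, and fainting or bleeding can be seen. Capture is passive, but not left to chance. Needling pain and a late bruise are less visible.

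It is also fair to say that no objective commits the trial to estimating a reaction rate. The percentages above therefore do not correct any figure in the plan.

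**Conclusion.** The point holds in a limited form. Section 7.5 has no usable end point, and 7.3 and 7.4 provide none for non-serious AEs. The statements on IRB reporting in 5.1, 7, 7.4 and 7.5 need to be reconciled. None of the four listed reactions is asked about on any ED form reproduced in Appendix B, so reactions confined to the ED depend on staff awareness and may be under-counted. The extent of any under-count cannot be estimated from the documents.

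The 3.9% bound (4.9% at an assumed 60 treated) shows only what asking every patient would buy. It rests on the stated number treated and on complete ascertainment. The form finding rests on the unreproduced records containing no equivalent prompt, which the sponsor can check at once.

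This should be corrected, but it does not threaten the recruitment and retention outcomes.

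**What to change.** 1. Rewrite the sentence in 7.5 so that follow-up runs from onset to the end point the sponsor intends, and make it agree with 7.3 and 7.4. In the same edit, reconcile the IRB reporting statements in 5.1, 7, 7.4 and 7.5. Which end point and which reporting rule apply is for the sponsor and the IRB to decide.
2. Check whether the AE log, session record or ED Visit Checklist already prompts for the four reactions. If one does, cite it in 7.2. If none does, add four yes/no fields to the coordinator-facing Post Acupuncture form, which is already completed from the acupuncturist.
3. Report the count for each reaction among patients who received acupuncture, with the exact binomial intervals that Section 9.5 already plans for categorical variables.

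The cost is a short text amendment and four tick-boxes per acupuncture patient. The fields apply to one arm only, so they describe the tolerability of needling and do not give a between-arm comparison of harms.
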